Subjects without sufficient data for the determination of response status (i.e., responder versus non-responder) will be treated as non-responders in the analysis. Every effort should be made during the conduct of the study to limit the extent of missing data. Subjects who prematurely discontinue the study drug should remain in the study for collection of data, unless the subject withdraws consent.

Alternative Primary Efficacy Endpoint:

The alternative primary efficacy endpoint is platelet response as defined by the proportion of subjects for whom at least 2 consecutive platelet assessments are $\geq 50 \times 10^9/L$ over the 12-week Treatment Period in the Core Phase in the absence of rescue medication. The null hypothesis is that the treatment effect of avatrombopag is the same as that of placebo. The alternative hypothesis is that the treatment effect of avatrombopag is different than that of placebo.

The alternative primary efficacy endpoint will be tested between avatrombopag and placebo using the Cochran-Mantel-Haenszel 2-sided test at α =0.05, adjusting for age cohort and Baseline platelet count (\leq 15× 10⁹/L vs >15×10⁹/L), or the Fisher's exact test, when data is sparse. In addition, the numbers and percentages of responders in each treatment group, the associated 95% CI, and the 95% CI for the difference between avatrombopag and placebo will be summarized. The primary analysis will be performed based on the FAS and repeated on the PPS as a supportive analysis. Other sensitivity analyses of the alternative primary efficacy endpoint may be performed as appropriate.

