3.2 Study Endpoints

3.2.1 Efficacy Endpoints

• Primary Efficacy Endpoint

Durable platelet response defined as the proportion of subjects achieving at least 6 out of 8 weekly platelet counts ≥50×10⁹/L during the last 8 weeks of the 12 week Treatment Period in the Core Phase in the absence of rescue medication

• Alternative Primary Efficacy Endpoint (per EMA PIP)

Platelet response as defined by the proportion of subjects for whom at least 2 consecutive platelet assessments are ≥50×10⁹/L over the 12 week Treatment Period in the Core Phase in the absence of rescue medication

Additional Secondary Efficacy Endpoints

- The percentage of weeks subjects have a platelet count ≥50×10⁹/L during 12 weeks of treatment in the Core Phase, in the absence of rescue therapy.
- Platelet response at Day 8 (defined by the proportion of subjects with a platelet count $\geq 50 \times 10^9$ /L at Day 8, in the absence of rescue therapy).
- The percentage of weeks subjects have a platelet count between ≥50×10⁹/L and ≤150×10⁹/L, during 12 weeks of treatment in the Core Phase, in the absence of rescue therapy.
- The proportion of subjects who require rescue medications during 12 weeks of treatment in the Core Phase of the study.
- Incidence and severity of bleeding symptoms associated with ITP measured using the WHO Bleeding Scale

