5. PLANNED ANALYSIS

5.1 Changes from Planned Analyses in the Protocol

An exploratory efficacy endpoint was included which was not detailed in the protocol: Month 3 durable platelet response defined as the proportion of subjects achieving at least 3 out of 4 weekly platelet counts $\geq 50 \times 10^9$ /L during the last 4 weeks of the 12 week Treatment Period in the Core Phase in the absence of rescue medication.

Bleeding Adverse Events of Special Interest identified using a MedDRA SMQ were further defined as clinically significant blood loss using reported CTCAE grades instead of WHO bleeding grades, as WHO bleeding grades collected at study visits are not linked to individual adverse events.

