7.4 Efficacy Analysis

Unless otherwise stated, all primary and secondary efficacy endpoints defined in Section 3.2.1 will be analyzed for the FAS and PPS.

For the efficacy evaluation of the platelet count responses, platelet counts assessed by local labs will be used. Platelet counts collected via the central lab will be used in the safety assessments of

clinical laboratory tests.

The methods used for efficacy analysis for the Core Phase are summarized in Error! Reference source not found.3. All Cochran-Mantel-Haenzel (CMH) tests at alpha=0.05 within each age cohort will be performed adjusting for baseline platelet count category ($\leq 15 \times 10^9 / L \text{ vs} > 15 \times 10^9 / L$). For the CMH test in the overall group, the test will be performed adjusting for age cohort and baseline platelet count category. Fisher's exact test will be used if the number of durable platelet responders is spare in the strata (less than 3 in a specific subgroup). Durable platelet response with 2-sided 95% exact binomial (Clopper-Pearson) confidence interval (CI) will be provided. The difference in response rate (avatrombopag – placebo) with 2-sided 95% CI (Wald) will also be provided.

Subjects without sufficient data for the determination of response status (i.e., responder versus non-responder) will be treated as non-responders in the analysis.

For the primary efficacy endpoint determination, a subject must have remained in the Core phase through at least Week 10 (to have at least 6 weeks of platelet count data starting from week 5 to either week 12 if the subject completes the core phase or the last week if the subject prematurely terminates the core phase). If a subject terminates the Core phase prior to Week 10, they would be considered a non-responder for the primary efficacy endpoint.

Endpoint	Analysis Method
Primary Efficacy Endpoint	
Durable platelet response defined as proportion of subjects achieving at least 6 out of 8 weekly platelet counts $\geq 50 \times 10^9 / L$ during the last 8 weeks of the 12 week treatment period in the Core Phase in the absence of rescue medication. In the case of rescue medication being used, platelet count assessments from the start date of rescue medication up until 4 weeks after the end date of rescue medication will be excluded from analysis.	CMH test

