Alternative Primary Efficacy Endpoint • Platelet response defined as proportion of subjects for whom at least 2 consecutive platelet assessments are ≥50×10 ⁹ /L during last 8 weeks of the 12 week treatment in the Core Phase in the absence of rescue medication	CMH test

Secondary Efficacy Endpoints

Percentage of weeks subjects have a platelet count $\geq 50 \times 10^9 / L$ during 12 weeks of treatment in the Core Phase, in the absence of rescue therapy. Denominator for this calculation is based on the number of weeks the subject was on treatment (up to 12 weeks)

CMH test

tests

Nonparametric

Wilcoxon Rank Sum

Platelet response at Day 8 (defined by the proportion of subjects with a platelet count $\geq 50 \times 10^9 / L$ at Day 8, in the absence of rescue therapy)

Endpoint	Analysis Method
• Percentage of weeks subjects have a platelet count between ≥50×10 ⁹ /L and ≤150×10 ⁹ /L, during 12 weeks of treatment in the Core Phase, in the absence of rescue therapy. Denominator for this calculation is based on the number of weeks the subject was on treatment (up to 12 weeks)	Nonparametric Wilcoxon Rank Sum tests
• Proportion of subjects who require rescue medications during 12 weeks of treatment in the Core Phase of the study	CMH test
• Overall incidence and incidence of severe bleeding symptoms (scale 3 and 4) associated with ITP measured using the WHO Bleeding Scale	CMH test
Exploratory Efficacy Endpoint	
• Month 3 durable platelet response defined as the proportion of subjects achieving at least 3 out of 4 weekly platelet counts ≥50×10 ⁹ /L during the last 4 weeks of the 12 week Treatment Period in the Core Phase in the absence of rescue medication	CMH test

Note: Fisher's exact test will be used if CMH test fails.

If the test of the treatment effect on the primary efficacy endpoint is statistically significant, the statistical tests on the secondary efficacy endpoints will be considered inferential; otherwise, the tests will be considered descriptive and no statistical inference can be drawn with regards to the secondary efficacy endpoints.

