To control the family-wise Type I error rate at a significance level of $\alpha = 0.05$ (2-sided), a step-down closed testing procedure will be used when testing the secondary efficacy endpoints. Starting with the key secondary efficacy endpoint, if the test is significant at $\alpha = 0.05$, then the test on the next endpoint will be considered inferential; otherwise, the tests on the subsequent endpoints will be considered descriptive only. This process will be repeated from the top of the hierarchy for the remaining endpoints.

The efficacy variables collected during the Open Label Extension Phase will be summarized descriptively.

For the Core Phase, observed values and change from baseline over time for platelet counts will be summarized. For the Core Phase, WHO bleeding scale will be summarized by visit.

For the Extension phase, observed values for platelet counts and WHO bleeding scale will be summarized by visit.

Blood product transfusions will be summarized for both the Core Phase and the Open Label Extension Phase including the following variables:

- Number and percentage of subjects with at least one blood product transfusion
- Total number of blood product transfusions
- Type of blood product
- Reasons for transfusion
- Number of packs/units per transfusion

Platelet count and blood transfusions will be listed for the Full Analysis Set.

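### SAP Table 3 counts the alternative primary endpoint over the last 8 weeks only, whereas the protocol and SAP 3.2.1 define it over all 12 weeks

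*SAP*

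**What the plan says.** Protocol 3.2 and the synopsis define platelet response as at least two consecutive assessments at or above 50×10⁹/L across the 12-week Treatment Period without rescue. Protocol 11.2.2 repeats this in the analysis section: "over the 12-week Treatment Period in the Core Phase in the absence of rescue medication". SAP 3.2.1, which labels the endpoint as the one required by the EMA PIP, agrees: "over the 12 week Treatment Period in the Core Phase in the absence of rescue medication".

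SAP 7.4, Table 3, the method table for the Core Phase, gives a different window for the same endpoint: "during last 8 weeks of the 12 week treatment in the Core Phase in the absence of rescue medication". The text of 7.4 shows that the last 8 weeks are Weeks 5 to 12. For the durable-response endpoint it requires a child "to have at least 6 weeks of platelet count data starting from week 5 to either week 12".

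SAP 7.4 also opens by stating that "all primary and secondary efficacy endpoints defined in Section 3.2.1 will be analyzed for the FAS and PPS". SAP 5.1 lists two departures from the protocol: a new exploratory endpoint ("An exploratory efficacy endpoint was included which was not detailed in the protocol") and the grading of bleeding events of special interest. A shorter window for this endpoint is not among them.

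SAP 2.2 calls this endpoint the key secondary endpoint, and the step-down testing in 7.4 begins there: "Starting with the key secondary efficacy endpoint".

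**The concern.** One SAP holds two definitions of the same endpoint and no rule for choosing between them. Two programmers could produce different responder lists and each cite the SAP correctly.

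The difference falls on particular children. A child with two consecutive counts at or above 50 in Weeks 1–4 who then loses response is a responder under the protocol and a non-responder under Table 3. The same holds for an early responder who leaves the Core Phase before Week 6, because a pair within Weeks 5–12 needs counts at both Week 5 and Week 6 at the earliest. Early response followed by loss is plausible in this design. Protocol Table 3 reduces study drug above 150×10⁹/L and stops it above 250×10⁹/L, and protocol 8.4 lets background ITP medication be reduced.

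At stake are the estimate, its confidence interval and its traceability to the protocol, for an endpoint that carries a regulatory label and opens the secondary hierarchy. If Table 3 is followed, the rate reported here could also differ from the rate in the second SAP, where the protocol makes this endpoint primary.

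**Working it through.** **1. The plan's own figures.** Inputs (SAP 2.2, protocol 11.3): 54 avatrombopag and 18 placebo, Fisher's exact test, α = 0.05; protocol 11.2.2 gives two-sided testing. Power is the sum of Bin(a; 54, p₁) × Bin(b; 18, p₂) over all 55 × 19 outcomes with p ≤ 0.05.

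- Difference of 80 points (80% vs 0%, 88% vs 8%, 90% vs 10%): above 99.9%. Stated: at least 99%.
- Durable response, 41.3% vs 3.4%: 94.5%. Stated: at least 90%.

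Both reproduce, so the sample size is not in question. The 88% behind the 80-point difference comes from a 12-week study.

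**2. What the window removes.** With one count per week, n weeks give n − 1 adjacent pairs.

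- Weeks 1–12: 12 − 1 = 11 pairs.
- Weeks 5–12: 8 − 1 = 7 pairs.
- Lost: 11 − 7 = 4 pairs (Weeks 1–2, 2–3, 3–4 and 4–5).

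Every pair in Weeks 5–12 is also a pair in Weeks 1–12, so every 8-week responder is a 12-week responder. The reverse does not hold.

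**3. Size under assumed models.** The documents give no weekly response pattern, so these are illustrations.

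*Two-state weekly chain.* Assume 40% of children at or above 50 in Week 1, then a constant weekly chance of gaining response (g) and of losing it (l). All 2¹² response sequences were enumerated. The last column, at least 6 of the 8 counts in Weeks 5–12, can be compared with the planned 41.3%.

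| g | l | Pair in Weeks 1–12 | Pair in Weeks 5–12 | Gap (points) | Implied durable response |
|---|---|---|---|---|---|
| 15% | 5% | 86.4% | 82.8% | 3.6 | 59.0% |
| 15% | 10% | 84.5% | 77.7% | 6.8 | 44.6% |
| 15% | 20% | 80.0% | 68.1% | 11.9 | 24.7% |
| 10% | 30% | 64.0% | 46.5% | 17.5 | 9.1% |

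The second row is the closest to the planned durable rate. Its gap is 0.068 × 54 ≈ 3.7 children in the avatrombopag arm.

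*Independent weeks.* Assume a constant chance q of a count at or above 50 each week, and take the probability of at least two consecutive successes in 12 and in 8 weeks.

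- q = 0.1: 9.7% vs 6.3%
- q = 0.3: 57.4% vs 42.2%
- q = 0.5: 90.8% vs 78.5%

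**4. Effect on the test.** By the formula in step 1, power is 99.8% at 60% vs 5% and 98.1% at 50% vs 5%. A loss of the size in step 3 would rarely change the decision.

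**The case against.** The wording conflict is not disputed. The objections concern its consequence.

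- **The SAP may cure itself.** Section 7.4 says it analyses the endpoints of 3.2.1, and Table 3 is presented as a summary of methods, so 3.2.1 could be read as supplying the definition. This stands as a limit: the 8-week version is tested only if Table 3 is followed. It is no cure, because Table 3 restates the definition in full and differently, and no precedence is given.
- **The regulatory consequence cannot be checked.** The PIP and the second SAP are not available. This stands. The claim is confined to this SAP, which applies the PIP label to the 12-week definition.
- **Large gaps need pessimistic inputs.** The 12- and 17-point cases imply durable response of 25% and 9%, well below the planned 41.3%. In the second, the share at or above 50 falls from 40% in Week 1 to 25% in Week 12, although dosing is titrated to maintain response. This stands, and about 7 points is the better-calibrated figure. It is still material for a reported response rate.
- **Early exit is narrow.** Under protocol Tables 3 and 4 the top dose level is reached at about Week 4. Exit for low counts then needs a further 7 days or more than 3 weeks, and children who otherwise stop drug should stay for data collection. This stands, and loss of response during follow-up is the more likely route.
- **The gate will not flip.** Agreed, as step 4 shows. The concern is the endpoint and its estimate.

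**Conclusion.** The concern holds. SAP Table 3 defines the alternative primary endpoint over Weeks 5–12. SAP 3.2.1 and three places in the protocol define it over Weeks 1–12, and SAP 5.1 does not declare the change. No other row of Table 3 departs from the window in SAP 3.2, so carry-over from the durable-response row above is the likely cause, though that is an inference.

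The shorter window discards 4 of 11 pairs and can only lower the response rate. The drop is about 7 points under the chain nearest the planned durable rate, and roughly 4 to 17 points across the chains tried. These figures rest on one count per week, an assumed 40% in Week 1 and constant transition rates; the true gap cannot be derived from the documents. The primary durable-response test is unaffected, and the key secondary test is very unlikely to change. It must still be fixed, because the rule as written defines a different endpoint from the protocol's.

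**What to change.** In SAP 7.4, Table 3, replace "during last 8 weeks of the 12 week treatment in the Core Phase in the absence of rescue medication" in the alternative primary endpoint row with "over the 12 week Treatment Period in the Core Phase in the absence of rescue medication", so that it matches SAP 3.2.1 and protocol 3.2 and 11.2.2. If the 8-week window was intended, declare and justify it in SAP 5.1 and align 3.2.1. Check that the second SAP uses the same window.

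Make the change before database lock and unblinding, since a window chosen afterwards would look data-driven. It costs one phrase in the SAP. No visit, sample or sample-size figure changes.

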11.2.2.1 Secondary Efficacy Analysis

The secondary efficacy endpoints for this study are:

- The percentage of weeks subjects have a platelet count $\geq 50 \times 10^9 / L$ during 12 weeks of treatment in the Core Phase, in the absence of rescue therapy.
- Platelet response at Day 8 (defined by the proportion of subjects with a platelet count $\geq 50 \times 10^9 / L$ at Day 8, in the absence of rescue therapy).
- The percentage of weeks subjects have a platelet count between $\geq 50 \times 10^9 / L$ and $\leq 150 \times 10^9 / L$, during 12 weeks of treatment in the Core Phase, in the absence of rescue therapy.
- The proportion of subjects who require rescue medications during 12 weeks of treatment in the Core Phase of the study.
- Incidence and severity of bleeding symptoms associated with ITP measured using the WHO Bleeding Scale.

The categorical variables (e.g., proportion) will be summarized and analyzed in the same manner as the primary efficacy endpoint. The continuous variables (e.g., percentage of weeks subjects have a platelet count $\geq 50 \times 10^9 / L$) will be analyzed using nonparametric Wilcoxon Rank Sum tests.

If the test of the treatment effect on the primary efficacy endpoint is statistically significant, the statistical tests on the secondary efficacy endpoints will be considered inferential; otherwise, the tests will be considered descriptive and no statistical inference can be drawn with regard to the secondary efficacy endpoints.

To control the family-wise Type I error rate at a significance level of α = 0.05 (2-sided), a step-down closed testing procedure will be used when testing the secondary efficacy endpoints. Starting with the first secondary efficacy endpoint, if the test is significant at α = 0.05, then the test on the next endpoint will be considered inferential; otherwise, the tests on the subsequent endpoints will be considered descriptive only. This process will be repeated from the top of the hierarchy for the remaining endpoints. The hierarchy of the closed testing will be defined in the SAPs.

The efficacy variables collected during the Extension Phase will be summarized descriptively. Additional efficacy analyses will be performed if deemed necessary. The details of the analyses will be described in the SAP that will be finalized prior to database lock.

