2.2 Sample Size Determination

The proposed sample size is based on the anticipated response rates for avatrombopag and placebo for the primary endpoint (durable response) and the key secondary endpoint (platelet response for 2 consecutive weeks).

Based on the eltrombopag PETIT2 study conducted in pediatric patients with chronic ITP, the durable response rates were 41.3% and 3.4% for eltrombopag and placebo, respectively (Grainger, 2015). It is reasonable to assume that the treatment effect of avatrombopag will be very similar to that of eltrombopag, due to both drugs being in the same class, having similar mechanisms of action, and treating similar patient populations (e.g., patients aged ≥ 1 to <18 years with relapsed or refractory disease after 1 or more previous treatments for ITP and a Baseline platelet count $<30\times10^9$ /L). With the 3:1 ratio of avatrombopag to placebo, a total of 72 subjects (54 avatrombopag and 18 placebo) will provide at least 90% power to detect a treatment difference of 37.9% in durable response at α =0.05, based on the Fisher's exact test.

In addition, a 12 week study of romiplostim in treating pediatric ITP patients showed that 88% of romiplostim treated subjects achieved a platelet count $\geq 50 \times 10^9 / L$ for 2 consecutive weeks (key secondary endpoint), whereas none of the placebo treated subjects achieved the same endpoint (Bussel, 2011). With the 3:1 ratio of avatrombopag to placebo, a total of 72 subjects (54 avatrombopag and 18 placebo) will provide $\geq 99\%$ power to detect a treatment difference of 80% in proportion of subjects achieving a platelet count $\geq 50 \times 10^9 / L$ for 2 consecutive weeks at $\alpha = 0.05$, based on the Fisher's exact test.

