2.3 Randomization and Blinding

During Day 1/Visit 2 of the Core Phase, after study eligibility has been confirmed, randomization assignment will be performed using interactive response technology (IRT). Randomization will be stratified by age cohort. Subjects will also be stratified by a baseline platelet count of $\leq 15 \times 10^9/L$ or $>15 \times 10^9/L$ to $<30 \times 10^9/L$ in order to ensure treatment groups are approximately balanced. Following randomization, study drug will be dispensed in a double-blind manner. The Sponsor, the subject, and the clinical site personnel will be blinded to the treatment assignment.

No randomization or blinding is necessary for the Extension Phase as all subjects will receive open-label avatrombopag.

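### The two percentage-of-weeks endpoints use an unstratified Wilcoxon test despite stratified randomisation; the test stays valid, but a stratified rank test is a cheap safeguard (low severity)

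*SAP*

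**What the plan says.** SAP Section 2.3 sets two randomisation factors: "Randomization will be stratified by age cohort", and "Subjects will also be stratified by a baseline platelet count of" at most 15, or above 15 and below 30 (×10⁹/L). With three cohorts this makes six strata. SAP Section 2.2 plans "a total of 72 subjects (54 avatrombopag and 18 placebo"); Cohort 3 has 12 and 4.

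For binary endpoints, SAP Section 7.4 says: "For the CMH test in the overall group, the test will be performed adjusting for age cohort and baseline platelet count category". Two qualifications follow in the same section. CMH tests "within each age cohort will be performed adjusting for baseline platelet count category" use that one factor. The fallback uses neither factor: "Note: Fisher's exact test will be used if CMH test fails".

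For percentage of weeks at or above 50 and percentage of weeks from 50 to 150, Table 3 names "Nonparametric Wilcoxon Rank Sum tests". Protocol Section 11.2.2.1 agrees: continuous variables "will be analyzed using nonparametric Wilcoxon Rank Sum tests". Neither document mentions strata or covariates for this test, or explains the difference from the CMH tests.

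Secondary endpoints are tested step-down at 0.05, and only if the primary endpoint is significant. The protocol leaves the order to the SAPs. This SAP says to begin with the key secondary endpoint and states no order after it.

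**The concern.** Stratified randomisation makes the arms alike on the stratification factors. If those factors predict outcome, the treatment contrast no longer carries their variation, but an unstratified test still counts that variation in its standard error. The test then rejects too rarely under the null and can give up power under the alternative.

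Two of the seven primary and secondary endpoints in Table 3 are affected. If the listed order is the testing order, a miss on weeks at or above 50 would leave Day 8 response, weeks 50-150, rescue and bleeding descriptive. A miss on weeks 50-150 would leave rescue and bleeding descriptive.

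**Working it through.** **The plan's own figure.** The documents give no power for these two endpoints, so the check starts from the primary endpoint. Power of Fisher's test = Σ Bin(a; 54, 0.413) × Bin(b; 18, 0.034), summed over all tables with two-sided p ≤ 0.05. The result is 94.5%, which agrees with the stated figure of at least 90%.

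**Tests compared.** Each statistic is T²/Var(T), with R the rank, n₁ and n₀ the arm sizes, N = n₁ + n₀, and S² the sample variance of the ranks (so ties are handled). Subscript h denotes a stratum.

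- Unstratified Wilcoxon: T = Σ over active of (R − R̄); Var = (n₁n₀/N) S². S² includes the between-stratum spread.
- Stratified, overall ranks: T = Σₕ Σ over active in h of (R − R̄ₕ); Var = Σₕ (n₁ₕn₀ₕ/Nₕ) Sₕ². Between-stratum spread drops out.
- Van Elteren: the same, with ranks taken inside each stratum and weight 1/(Nₕ + 1).

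**Inputs.** From the documents: 54 vs 18, cohorts 21:7, 21:7 and 12:4, two platelet categories, 12 weekly counts, α = 0.05. Assumed, because the documents give nothing: a near-even platelet split (active:placebo 11:4, 10:3, 10:3, 11:4, 6:2, 6:2), a logit-normal weekly response with between-child SD 1.2, placebo intercept −1.5, treatment effect 1.2 logit, and platelet-stratum effects of 0, ±0.5 or ±1 logit. This treatment effect is smaller than planned; it implies durable response of about 22-27% vs 5-10%.

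| Platelet effect (logit) | Type I error, unstratified | Power, unstratified | Power, van Elteren | Power, overall ranks |
|---|---|---|---|---|
| 0 | 5.4% | 87% | 85% | 87% |
| ±0.5 | 3.8% | 82% | 84% | 85% |
| ±1 | 1.3% | 68% | 81% | 82% |

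The gain from overall ranks is 87 − 87 = 0, 85 − 82 = 3 and 82 − 68 = 14 points.

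**At the planned effect.** With the same model recalibrated to 41.3% vs 3.4%, unstratified Wilcoxon and van Elteren both have at least 99.9% power at 0, ±0.5 and ±1 logit. A separate simulation anchored on 41.3% vs 3.4%, with a platelet-stratum odds ratio from 1 to 9, gives 99.5-99.9% (unstratified), 98.6-99.9% (van Elteren) and 99.3-99.9% (overall ranks). With active response lowered to 28%, the ranges are 97.1-98.8%, 95.5-98.9% and 96.9-98.9%.

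**Cost when the strata say little.** In a further logit simulation with about 35% vs 13% of weeks and no stratum effect, power is 86.6% (unstratified), 85.4% (van Elteren) and 86.1% (overall ranks). With very strong strata (about 39% vs 20% of weeks) it is 68.4%, 78.7% and 80.1%. At still smaller treatment effects and no stratum effect it is 62.2%, 59.6% and 61.3%, or 49.0%, 46.1% and 48.6%. So with no stratum information overall ranks lose under 1 point (at most 62.2 − 61.3 = 0.9) and van Elteren about 1 to 3 (49.0 − 46.1 = 2.9). The least favourable run has a weak stratum effect and a very small treatment effect: 51.7%, 46.2% and 48.8%, a cost of 2.9 points for overall ranks and 5.5 for van Elteren. These simulations used 1,500 to 3,000 runs per scenario, so the Monte Carlo standard error near 85% is at most √(0.85 × 0.15/1500) = 0.9 points.

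**The case against.** The strongest reply is that the gain appears only where the plan's own assumptions fail. In the smaller-effect model, Fisher's test on durable response, which is the documents' power basis, has only about 23-26% power. The secondary sequence would then usually never open, so a 14-point gain further down seldom matters. This largely stands and is why the point is minor. It is not complete, because the planning effect is borrowed from eltrombopag durable response and the documents state none for these endpoints. Weeks 50-150 also drops weeks above 150, which should fall mainly on active drug, so its contrast may be smaller. In one smaller-effect run with strong strata, where the chance that a responding week exceeded 150 was assumed to rise with response up to 60%, power was 49.6% unstratified and 59.6% with overall ranks.

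The second reply is that the Wilcoxon test is prespecified, identical in both documents and protects type I error. That stands: the choice is between two valid tests.

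The third is that van Elteren is weak in strata this small. That stands for van Elteren, and only slightly for overall ranks.

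A reader might also infer more than the documents support:
- That every CMH test adjusts for both factors. The within-cohort tests use platelet category only, and Fisher's test uses neither.
- That half of the endpoints go unadjusted. It is two of seven.
- That the strata were chosen because they are expected to be prognostic. The stated purpose is approximate balance between arms.
- That a miss on either test would demote Day 8 response. Weeks 50-150 is listed after Day 8.

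**Conclusion.** The inconsistency is real: the overall binary tests use both randomisation factors and the two rank tests use neither. Validity is not at stake. It would be tempting to say that two steps of the sequence lose power, but the documents give neither a stratum effect nor a distribution for these endpoints, and at the planned effect the loss is nil. A loss of about 3 to 14 points arises only if the platelet strata act at about ±0.5 to ±1 logit and the treatment effect is also well below plan. Those inputs, the near-even platelet split and the logit-normal model are assumptions. The knock-on effect for later endpoints also assumes that the listed order is the testing order. This is a low-severity, low-cost improvement.

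**What to change.** Before unblinding, amend SAP Table 3 and protocol Section 11.2.2.1. For the overall comparison of both percentage-of-weeks endpoints, replace the Wilcoxon test by a rank test stratified by age cohort and baseline platelet category. The preferred form is a stratified CMH mean-score test with ranks computed once over all children, because some strata hold only about two placebo children. Van Elteren is an acceptable alternative. For any within-cohort comparison, stratify by platelet category alone, as the CMH tests already do.

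The change is one line of text in each document. The statistical cost is the small power loss shown above if the strata carry little information. Under SAP Section 7, an analysis designed after database lock would count as post hoc.
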